3.6 Randomization Method and Masking

Consenting women will be assigned to pravastatin or placebo in a 1:1 ratio according to a randomization sequence prepared and maintained centrally by the Biostatistical Coordinating Center (BCC). The two study medication arms of the study (pravastatin or placebo) are double masked; neither the patient nor the clinical staff will be aware of the treatment assignment.

The simple urn method will be used to generate the randomization sequences because it provides a high probability of balance in treatment assignments, it is unpredictable, and it allows an explicit randomization analysis to be conducted with relative ease.¹⁰³ Randomization will be stratified by clinical site to assure balance between the two treatment groups with respect to anticipated differences among the clinic population and possible differences in patient management.

4 Study Procedures

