4.3 Baseline Procedures

In addition to information collected for eligibility, project gestational age, and project EDD determination, the following information will be obtained at randomization from a patient interview followed by a review of her chart:

- Demographic information: age, race, ethnicity, insurance status
- Medical history: pre-pregnancy weight, height, medication use (e.g., aspirin, calcium, vitamins, anti-platelet agents, prior statins, antihypertensives), blood pressure, and thyroid and chronic disease history.
- Obstetrical history including outcomes of all prior pregnancies and which pregnancy(ies) was complicated by preeclampsia.
- Social history including marital status, years of education, alcohol and tobacco use.

During the randomization visit, blood pressure, height and weight will be recorded. Blood (27 ml) will be collected for Creatine Kinase (CK) and run in real-time at the local laboratory to serve as a reference in the event the patient develops a condition that suggests the possibility of myopathy and a repeat CK is warranted (Section 4.5). The remainder of the sample will be stored for analysis of DNA, lipids and

angiogenic markers. Proteinuria status at baseline is required for assessment of the primary outcome. Proteinuria will be evaluated by dipstick if not available from a recent prenatal visit. Dipstick values of 1+ or higher will require a protein:creatinine ratio or 24-hour urine collection for confirmation if not done clinically.

Treatment will be initiated at the randomization visit between 12 weeks 0 days and 16 weeks 6 days, in order to 1) avoid the period of organogenesis, and 2) start as early in pregnancy as possible. Treatment will start the same day as randomization, and the patient will be asked to take one capsule daily orally, with or without food. Treatment will continue until delivery or until a condition develops requiring discontinuation of the study drug.

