4.4 Study Procedures

All patients will have monthly assessments (in-person or virtual) with a research nurse to assess drug side effects and the occurrence of adverse events, and compliance by pill count. Patients will receive a 35 day supply of study drug to last until their next visit (in case it is slightly more than 4 weeks). Specifically, at each study visit, the following procedures will be performed:

- Assess drug side effects and adverse events
- Record weight
- Record blood pressure
- Perform pill count and dispense new supply
- Record current medication list

Treatment will continue until delivery or until a condition develops requiring discontinuation of the study drug (see Section 4.5). Blood will be collected and stored for retrospective analysis at two time periods, 1) 23-28^{6/7} weeks gestation and 2) at 33-37^{6/7} weeks gestation to measure lipids, angiogenic markers and pravastatin concentration (20 ml). Cord blood will be collected at delivery for the first 50 women randomized to measure pravastatin concentration (6 ml).

Table 4. Study visit procedures

	Timing	Procedures
Screening	< 16 ^{6/7} weeks	Consent, AST/ALT (if not available), verify eligibility criteria
Randomization	12 ^{0/7} -16 ^{6/7} weeks	Baseline data, record blood pressure and weight Blood collected for: 
 • Creatine Kinase (to be run immediately) • lipid profile(to be run at the end of study) • angiogenic markers (to be run during study) • maternal DNA (may be run in future)
Study visits	Monthly	Assessment of side effects, pill count, record BP and weight
	23 ⁰ -28 ^{6/7} weeks	Blood collected for: 
 • lipid profile (to be run at the end of study) • angiogenic markers (to be run during study) • maternal pravastatin concentration (may be run in future)
	33 ⁰ -37 ^{6/7} weeks	Blood collected for: 
 • lipid profile (to be run at the end of study) • angiogenic markers (to be run during study) • maternal pravastatin concentration (may be run in future)

Delivery		Clinical outcomes (maternal and neonatal) Cord blood collected for pravastatin concentration (first 50 only)
Postpartum	6 weeks postpartum	Assessment of adverse events, postpartum complications, record blood pressure and weight
Child Two-year Follow-up	2 years of age	Medical history, height and weight Cognitive, behavior, motor, visual and hearing assessment

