6.3 Analysis Plan

All statistical analyses will be based upon the total cohort of patients randomized into the trial. Although data on some patients may be missing, all relevant data available from each patient will be employed in the analyses. Patients will be included in the treatment group to which they were randomly assigned regardless of compliance.

The primary analysis will consist of a simple comparison of binomial proportions. The relative risks and confidence intervals will be reported. If the treatment groups are found to differ on a pre-treatment factor known to be a risk factor for the outcome, the statistical analysis will adjust for these differences, using a log binomial regression (or log-Poisson when relevant). An evaluation of treatment by center interaction will be included, using the Breslow-Day test. An analysis adjusting by center also will be performed to ensure that center differences do not change the conclusion.

If the primary outcome is significant or the trial is stopped early for benefit, the methods of Maurer and Bretz will be used to test formally the major secondary endpoint of preterm delivery < 37 weeks, while controlling the familywise error rate.¹²⁰

Loss to follow-up will be defined as the inability to ascertain whether a woman has preeclampsia. Those defined as lost to follow-up will not be included in the primary analysis. It is expected that the loss to follow-up rate will be very low. However, a sensitivity analysis will be performed including patients lost to follow-up with different assumptions regarding their outcome, to determine whether the results are

robust. Multiple imputation techniques (or a Bayesian bootstrap technique if the ‘missingness’ is non-ignorable) will be evaluated if required.¹²¹

Since many of the secondary endpoints are dichotomous variables like the primary outcome, standard statistical methods for rates and proportions will be appropriate. For normally distributed continuous outcomes, least squares means general linear regression will be used to estimate means and 95% confidence intervals. The Wilcoxon test and the Hodges-Lehmann estimators will be used to compare non-normal continuous variables that cannot be transformed to approximate normality. For time-to-event variables, the log-rank test and Cox proportional hazards model will be used (model assumptions tested by Lin’s test).

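### Section 6.3 names no baseline covariate for the angiogenic and lipid outcomes, although the same markers are sampled at randomization; specifying baseline-adjusted analysis would be a minor gain in precision

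*Combined protocol and SAP*

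**What the plan says.** Section 6.3 covers all normally distributed continuous secondary outcomes in one sentence: "For normally distributed continuous outcomes, least squares means general linear regression will be used to estimate means and 95% confidence intervals". Wilcoxon and Hodges-Lehmann methods are kept for "non-normal continuous variables that cannot be transformed to approximate normality". Neither sentence mentions a baseline value.

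Section 6.3 makes two provisions for covariates, both in the paragraph on the primary analysis. If the arms differ on a known pre-treatment risk factor, "the statistical analysis will adjust for these differences, using a log binomial regression (or log-Poisson when relevant". An analysis adjusted for center is also planned, whatever the balance. On missing data, the section says that "all relevant data available from each patient will be employed in the analyses".

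The baseline measurements are planned. Section 4.3 says of the blood taken at the randomization visit: "The remainder of the sample will be stored for analysis of DNA, lipids and" angiogenic markers. The randomization row of Table 4 schedules the assays, with lipids at the end of the study and "angiogenic markers (to be run during study". Section 4.4 adds two later draws, at 23-28 6/7 and 33-37 6/7 weeks, "to measure lipids, angiogenic markers and pravastatin concentration (20 ml".

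The angiogenic profile is a secondary research question in 3.2. Both marker sets are maternal secondary outcomes in 4.6.2 (items 13 and 14), with no time point, scale or baseline handling given. In 3.6, "Randomization will be stratified by clinical site".

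**The concern.** The baseline value of a biomarker is usually a useful predictor of its later value, and here it is collected anyway. A plan that does not commit to using it leaves two analyses open, with and without baseline, and the one without is less precise. The angiogenic assays are run during the study, so the choice is best fixed before any of those results can be seen by arm.

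A smaller reporting matter goes with it. Section 6.3 bases all analyses on the total randomized cohort, but a woman who has already delivered cannot give a 33-37 6/7 week pregnancy sample. The trial hopes to change delivery timing, and 2.2.1 links sFlt-1 and sEng to later disease. No section says that the late contrast is restricted to women still pregnant.

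At stake are the width of the confidence intervals for these markers and the wording of one contrast.

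**Working it through.** **Inputs.** From the documents: 1,550 women (6.2) allocated 1:1 (3.6), so 775 per arm, and two-sided 5% error (6.2). The 80% power level is the one that 6.2 uses for secondary outcomes. Assumed: the baseline-to-follow-up correlation ρ, taken as 0.3, 0.5 and 0.7.

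**1. The plan's own figure.** The plan gives no power or precision figure for these markers, so only the 1,550 can be checked. With 5% of the pravastatin arm at the placebo rate, that arm's rate is 0.95 × 0.14 + 0.05 × 0.20 = 0.143. With unpooled variance, n per arm = (1.960 + 1.036)² × (0.20 × 0.80 + 0.143 × 0.857) / 0.057² ≈ 781, or 1,562 in all, which is 0.8% above 1,550. A factor of 1.019 for the two interim looks gives 1,592, or 2.7% above. I take 775 per arm as given.

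**2. Precision.** ANCOVA multiplies the variance by (1 − ρ²). The detectable difference in SD units is 2.80 × √(2/775) × √(1 − ρ²), and 2.80 × √(2/775) = 0.142. The equivalent unadjusted n per arm is 775/(1 − ρ²). Power at a true difference of 0.10 SD is Φ(0.10/SE − 1.96), where the unadjusted SE is √(2/775) = 0.0508.

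| ρ (assumed) | Variance removed | Detectable difference (SD) | Equivalent n per arm | Power at 0.10 SD |
|---|---|---|---|---|
| 0 (unadjusted) | 0% | 0.142 | 775 | 50% |
| 0.3 | 9% | 0.136 | 852 | 54% |
| 0.5 | 25% | 0.123 | 1,033 | 62% |
| 0.7 | 49% | 0.102 | 1,520 | 79% |

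Confidence intervals narrow by 1 − √(1 − ρ²), which is 4.6%, 13.4% and 28.6%.

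**3. The late window.** Fewer women are sampled at 33-37 6/7 weeks. Section 6.2 claims at least 80% power for a 40% reduction in delivery before 34 weeks. With 775 per arm, 80% power corresponds to about 9.4% against 5.6%. These rates are inferred, and delivery before 34 weeks is only a proxy for a missed draw. They leave 775 × 0.906 = 702 and 775 × 0.944 = 732 women, an SE of √(1/702 + 1/732) = 0.053, and detectable differences of 0.148, 0.141, 0.128 and 0.106 SD for ρ = 0, 0.3, 0.5 and 0.7.

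**4. Attenuation from conditioning on ongoing pregnancy.** Let the marker and a latent tendency to early delivery be bivariate normal with correlation r. If a proportion p has delivered, the mean among the rest is −r × φ(z)/(1 − p), with z = Φ⁻¹(1 − p). The difference between arms, for r from 0.3 to 0.7:

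- 9.4% vs 5.6% (inferred above): r × (0.185 − 0.120), about 0.02 to 0.05 SD.
- 15% vs 10% (assumed): about 0.02 to 0.06 SD.
- 20% vs 5% (indicated delivery before 34 weeks in the pilot, Table 2, 4/20 vs 1/20): r × (0.350 − 0.109), about 0.07 to 0.17 SD.
- Equal rates: zero.

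The shift is toward no difference for a marker that pravastatin lowers.

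**5. What baseline adjustment does to that shift.** In a simulation of 4 million women per setting, with marker-to-propensity and baseline-to-late correlations both assumed to be 0.5, ANCOVA removed about 0%, 15%, 29% and 46% of it at baseline-to-propensity correlations of 0, 0.15, 0.3 and 0.5.

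**The case against.** The strongest reply is that 6.3 contains no error. A linear model with least squares means readily carries covariates, transformation is allowed, and the baseline value of a marker can be read as part of the relevant data the section promises to use. One generic sentence for a long list of secondary outcomes is a choice about level of detail. This stands. A reader might infer that the plan rules out baseline adjustment, or that an unadjusted comparison would be invalid. The documents support neither: the text is silent, and randomization protects the unadjusted contrast where all women are sampled. But permission is not commitment, and two analyses still fit the wording.

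A second reply is that precision is already ample. The unadjusted detectable difference is 0.142 SD, and no section sets a target effect for these markers. The pilot's 20 mg LDL difference, 97.5 − 91.2 = 6.3 mg/dL on a pooled SD of √((29.3² + 40.8²)/2) = 35.5, is 0.18 SD and has 94% power unadjusted (raw scale, 10 women per arm). This also stands, and it rules out the inference that the trial is underpowered for these outcomes.

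A third reply is that the late-window figures rest on inferred rates and assumed correlations, and that a window defined in weeks of gestation already makes the condition evident. Both are fair. They leave the condition as a reporting note only.

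**Conclusion.** The point holds as a minor improvement to secondary outcomes. Section 6.3, applied as written, need not use baseline values that the trial collects, and so may give up 9% to 49% of the variance at assumed correlations of 0.3 to 0.7. The documents give no correlation. At 0.3 the gain is slight, and at 0.7 it is worth as much as nearly doubling the sample. These figures assume that all 775 women per arm have both samples.

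The late contrast is conditional on ongoing pregnancy for lipids as well as angiogenic markers, since both come from the same draw. A reader might infer that it is materially biased. The documents do not support that: across the assumed delivery rates and correlations the attenuation runs from about 0.02 to 0.17 SD, it is zero if delivery timing does not differ, and nothing in the plan narrows the range.

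Nothing here touches the primary analysis, the 1,550 or the formal testing of preterm birth before 37 weeks.

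**What to change.** Add to 6.3:

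- Angiogenic and lipid concentrations at 23-28 6/7 and 33-37 6/7 weeks are compared by ANCOVA, or by a repeated-measures linear model with treatment, window and their interaction. Either model adjusts for the baseline value of the same marker and for clinical site, the stratification factor.
- The log scale is used where the section's own normality rule calls for transformation. It need not be imposed on every lipid.
- Women without a usable baseline sample are kept by a simple stated rule, such as a missing-baseline indicator or mean imputation.
- Results for both marker sets at 33-37 6/7 weeks are described as conditional on ongoing pregnancy. This note is needed with or without adjustment, because adjustment removes only part of any attenuation.

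The cost is wording, since the samples and assays are already planned. There are two small drawbacks: markers analysed on the log scale are reported as ratios of geometric means, and the missing-baseline rule needs a line of its own. The text should be settled before any angiogenic results are seen by arm.

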6.3.1 Subgroup Analyses

If the two groups show a difference in the incidence of the primary outcome or major secondary outcome, interactions will be evaluated and subgroup analyses conducted to determine whether the effect prevails throughout particular subgroups of patients. Indeed, NIH guidelines require investigators to evaluate consistency between the genders and across racial subgroups. It should be noted, however, that subgroup analyses have been greatly abused, particularly when there is no overall treatment difference.¹²² There is a strong temptation to search for a specific subpopulation in which the therapy is nevertheless effective. Yusuf et al. concluded “*the overall ‘average’ result of a randomized clinical trial is usually a more reliable estimate of the treatment effect in the various subgroups examined than are the observed effects in individual subgroups.*”¹²³ Thus subgroup analyses will be interpreted with care.

It is generally acknowledged that subgroup analysis that is pre-specified in the protocol has more validity than ad-hoc comparisons. The following factors will be considered for subgroup analysis, if there is a significant interaction between the factor of interest and the treatment effect:

- Race/ethnicity
- Baseline BMI category
- Gestational age at randomization
- Actual or prescribed aspirin use at baseline
- Pregestational diabetes
- Chronic hypertension at baseline
- Singleton pregnancy

For subgroup analyses, there will be more limited power. However, if an interaction test were positive for the primary outcome, indicating the presence of heterogeneity between subgroups, and 1) the subgroups were each 50% of the sample size and 2) the placebo outcome rate in the subgroup were the same as assumed overall (20%), then there would be more than 85% power to detect a 40% difference between treatment groups within one of the subgroups.

The racial/ethnic composition of women recruited into the MFMU Network trials varies. Assuming for this trial that the composition is 31% African-American and 24% Hispanic (estimates based on site specific rates reported among preeclamptics in the RCT of Antioxidants to Prevent Preeclampsia CAPPs trial) there is more than 85% power to detect a 50% reduction in the primary outcome in African American women and 77% power to detect a 50% reduction in the primary outcome in Hispanic women within these separate subgroups.

7 Data Collection

7.1 Data Collection Forms

Data will be collected on standardized forms on which nearly all responses have been pre-coded. Each form is briefly described below:

- Screening Log
- Eligibility and Randomization Form is completed for all patients eligible for the study.
- Study Drug Randomization Log: lists patients randomized to pravastatin or placebo, and provides the drug code number.
- Baseline Form is completed for all randomized patients. This form includes detailed demographic and social data, medical and obstetrical history, and current pregnancy complications.
- Previous Pregnancy Outcome Form
- Study Visit Form documents monthly study visits, possible side effects and compliance
- Creatine Kinase Log documents CK values reported for the participant.
- Study Drug Dispensing and Compliance Log documents the dispensing of study medication and the return of any unused study medication.
- Study Drug Alteration Log for Side Effects documents the modification of study medication due to side effects.
- Unscheduled Visit or Hospitalization Form is completed for all patients who had an unscheduled emergency room, Labor & Delivery, clinic visit or hospitalization between the scheduled monthly visits, including the delivery admission.
- Maternal Delivery and Outcome Form documents specific pregnancy complications since randomization, in addition to labor, delivery and postpartum information.
- Neonatal Baseline Form records date and time of birth, delivery data and status at delivery, for each fetus/infant.
- Neonatal Outcome Form records outcome data for all infants admitted to the NICU or special care nursery.
- Patient Status Form documents loss to follow up/withdrawal status, last date of contact for lost to follow-up patients, side effects since the last dose.
- Follow-up Visit Form documents maternal complications since discharge and the 6-week postpartum study visit.
- Postpartum Readmissions Log is completed for all patients who are readmitted to the hospital after discharge following delivery.
- Adverse Event Form records serious and non-serious adverse events.
- Outcome Diagnosis Form records outcome data for hypertension and preeclampsia
- Two Year Study Visit Form for infants and proprietary forms for neurodevelopmental and behavior testing

- Five Year Study Visit Form for infants and proprietary forms for neurodevelopmental and behavior testing

7.2 Web Data Entry System

For this protocol, web data entry screens corresponding to the study forms listed above will be developed and maintained by the staff of the BCC. Clinical center staff will enter data into the MySQL database located at the BCC through a web data management system (MIDAS). The data are edited on-line for missing, out of range and inconsistent values. A Users' Manual documenting this system is provided to the centers by the BCC.

7.3 Centralized Data Management System

Daily data conversions from the MySQL database create up-to-date SAS datasets. Data are reviewed weekly using edit routines similar to those implemented on-line during data entry, as well as additional checks for data consistency within or across forms. A database of resulting potential data problems is generated in MIDAS for initial review by BCC staff who then evaluate the comments keyed in association with edits on missing or unusual values. Valid edits will be flagged in MIDAS for resolution at the clinical centers.

At regular intervals, specialized data reviews comparing data availability and consistency across forms are run by the BCC staff on the entire database or on a specific subset of data. These reports are also submitted to the centers for correction or clarification.

An audit trail, consisting of all prior versions of each data form as entered in the computer for each patient, is maintained so that the succession of corrections can be monitored.

7.4 Performance Monitoring

The BCC will present regular reports to the Protocol Subcommittee, the Steering Committee, and the Data and Safety Monitoring Committee. These include:

- Monthly Recruitment Reports - reports of the number of women screened and enrolled by month and by clinical center are provided monthly to the subcommittee and all other members of the Steering Committee. Weekly or bi-weekly reports are provided electronically as decided by the Protocol Subcommittee.
- Quarterly Steering Committee Reports - reports detailing recruitment, baseline patient characteristics, data quality, incidence of missing data and adherence to study protocol by clinical center, are provided quarterly to the subcommittee and all other members of the Steering Committee.

8 Study Administration

